4.2. Study Design

4.2.1. Phase 1 Dose Escalation (Part A)

The primary objective of Part A is to determine the recommended Phase 2 dose (RP2D) of TAS3351 based on observed DLTs, safety, antitumor activity, PK, and pharmacodynamics. Part A of Study 10073010 will consist of a Dose Escalation part (Part A1) and a part for “Backfill” patients (Part A2)

Part A1: Dose Escalation

The Phase 1 Dose Escalation is designed to evaluate 6 dose levels of TAS3351 from 50 to 700 mg/day (Table 5) using a Bayesian Optimal Interval (BOIN) design. [REDACTED]

TAS3351 will be administered once daily (QD) on a 21-day cycle at a starting dose of 50 mg QD and escalated based on tolerability (see Section 6.1.1) to patients who harbor any EGFR mutation, with consideration of lower increments than planned if clinically relevant toxicities are observed (intermediate dose levels). In the event of unacceptable toxicities at Dose Level 1, lower dose levels may be explored (eg, Dose Level -1). If PK, pharmacodynamic, and/or safety data indicate, twice daily (BID) dosing of TAS3351 may be explored. In order to appropriately characterize the PK profile of TAS3351, there will be a PK lead-in with a single administration of TAS3351 followed by PK sampling 3 days prior to the start of continuous daily dosing of TAS3351 for patients enrolled in the Dose Escalation Part A1 only.

Part A2: Backfill Patients

When a dose level has been determined to be safe in Part A1 and preliminary antitumor activity has been observed, up to 10 further patients may be enrolled in that dose level (for a total of up to 20 backfill patients). A dose is deemed to be safe in Part A1 if there is an acceptable DLT rate in that dose level as per the BOIN design. Antitumor activity is defined as evidence of tumor shrinkage in at least one of the patients at that dose level.

If no preliminary antitumor activity is observed in Part A1, the totality of nonclinical in vitro and in vivo data as well as clinical PK data may be used to inform selection of dose level(s) for “backfill” patients. This will include IC₅₀ values from various in vitro assays and/or the total exposure of TAS3351 and its active metabolite associated with tumor shrinkage in preclinical xenograft mouse models to be used as thresholds for targeted efficacious C_{min} and/or AUC, respectively. The exposure linked with nonclinical activity is a total TAS3351 and TAS-05-14317 C_{min} of 40.3 nM. Clinical PK simulation will be applied to project dosing regimen(s) which may achieve the targeted threshold(s). The doses explored in the A2 part of the trial will be chosen in consultation between the investigators and the Sponsor based on the above safety and efficacy criteria as well as a review of the PK data. “Backfill” patients enrolled are required to have a tumor harboring a C797S *EGFR*mt. The additional information from these “backfill” patient cohorts will broaden the amount of safety and preliminary antitumor activity data for TAS3351 at potential active dose levels to inform the selection of the RP2D of TAS3351.

4.2.2. Phase 1 Dose Expansion (Part B)

The Phase 1 Dose Expansion part of the study will be initiated after an RP2D and a dosing scheme has been identified in Part A. NSCLC patients with C797S *EGFR*mt will be enrolled to explore the efficacy and confirm the safety of TAS3351 at the RP2D in a larger patient population. Moreover, a second dose level of TAS3351 may be evaluated in an additional cohort of patients in Part B if promising antitumor activity is observed at another lower TAS3351 dose level during Part A. In this case, patients enrolled in Part B will be randomized at a 1:1 ratio between the two treatment arms to evaluate the optimal RP2D of TAS3351 based on a comparative analysis considering the totality of efficacy and safety data observed.

The results from Part B will confirm the RP2D of TAS3351 and are expected to provide, in combination with the “Backfill” patients from Part A2, the proof of concept for the efficacy of TAS3351 in NSCLC patients with the C797S *EGFR*mt. Based on these results, the Phase 2 part of this study will be initiated.

In addition, further cohorts may be added by an amendment to explore the activity of TAS3351 in further subgroup(s) of patients based on activity observed in the Part A dose escalation and/or emerging scientific data. This may include an additional cohort for *EGFR*mt NSCLC patients with brain metastases to explore the efficacy of TAS3351 against CNS metastases or against other type of *EGFR*mt, if promising results are observed during Part A of this study.

4.2.3. Phase 2 (Part C)

The Phase 2 part of the study will be an open-label, single-arm, Phase 2 study to assess the safety and efficacy of TAS3351 in advanced NSCLC patients with C797S *EGFR*mt who progressed on a prior treatment with another EGFR inhibitor. Patients will receive TAS3351 at the RP2D and dosing scheme confirmed in Part B and be evaluated for ORR based on

RECIST v1.1 by Independent Central Review (ICR) as the primary endpoint. A key secondary endpoint of this part of the study will be duration of response (DoR) by ICR.

4.2.4. Study Stopping Criteria

The study will be stopped in the event of unacceptable toxicities. If the following toxicities are observed in at least 1 patient, dosing of new patients will be suspended until further review of safety to determine if dosing can resume. These toxicities will include, but are not limited to, the following:

- Any death other than disease progression in any patient in which the cause of death is judged to be at least possibly related to the study treatment by the investigator.
- Liver function test increase that is considered to be a Hy's Law case
- \geq Grade 4 severe cutaneous adverse reactions (Steven-Johnson syndrome, toxic epidermal necrolysis, erythema multiforme, acute generalized exanthematous pustulosis, drug rash with eosinophilia and systemic symptoms (DRESS) syndrome)

In Part A1, dosing of patients in a dose level will stop if there is an unacceptable DLT rate as per the BOIN design.

For the patients participating in Part A2 ("back-fill") and Part B (dose expansion), if adverse events meeting the DLT definition surpass 30% during Cycle 1 in a particular cohort, enrollment will be stopped for that cohort. Patients in other cohorts without such safety issues may continue dosing.

After approximately 25% of patients are enrolled in Part C, the data will be reviewed to determine if there are safety concerns that justify modification to or termination of the trial. Timing of subsequent reviews will depend on the rate of recruitment in this part of the study.

The Sponsor's medical monitor, in consultation with the study investigators, will decide following review whether suspension of patient accrual may be lifted and if any adjustments of the protocol are required prior to reopening enrollment. Prior to the start of Phase 2, a Data Monitoring Committee (DMC), including members external to the Sponsor, will be established (Section 4.12). The DMC will review all safety data after dose expansion before proceeding to Part C (Phase 2). The trial may be terminated by the Sponsor, if after discussion with the investigators or DMC, the benefit risk ratio is no longer favorable for patients.

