6.2.1.2. Dose Modifications for Non-hematologic Toxicities

Recommendations for dose modification due to study drug-related diarrhea, hepatic events, skin rash, QT prolongation, interstitial lung diseases (ILD), and other non-hematologic toxicities are presented in [Table 10](#).

Table 10: Recommendations for Managing Non-Hematologic Toxicities

Grade by CTCAE v5.0	Management Recommendation
Diarrhea (see also Section 6.4.4.2)	
Grade 1 and 2	No dose modifications required, initiate supportive therapy (see Section 6.4.4.2) If persistent / recurrent Grade 2 that does not resolve with maximal supportive measures, reduce to next lower dose level
Grade 3	Suspend dose until resolved to \leq Grade 2, then: 
 • If resolved ≤ 14 days, resume at the same dose level and consider anti-diarrheal prophylaxis • If resolved > 14 days or re-occurrence, resume at next lower dose level
Grade 4	Suspend dose until resolved to \leq Grade 1 or baseline, then resume at next lower dose level.
Hepatic events	
Bilirubin increased	
Grade 1 and 2	No dose modifications required Note: Assess AST and ALT for \geq Grade 2 bilirubin (see Hy's law below)
Grade 3	Suspend dose until resolved to \leq Grade 1 or baseline, then: 
 • If resolved ≤ 14 days, resume at the same dose level • If resolved > 14 days or re-occurrence, resume at the next lower dose level
Grade 4	Discontinue study drug
AST or ALT increase	
Grade 1 and 2	No dose modifications required NOTE: Assess bilirubin for \geq Grade 2 AST/ALT (see Hy's law below)
Grade 3	Suspend dose until resolved to \leq Grade 1 (\leq Grade 2 in the presence of liver metastasis) or baseline, then: 
 • If resolved ≤ 14 days, resume at the same dose level • If resolved > 14 days, resume at the next lower dose level
Grade 4	Discontinue study drug
Hy's law	
AST or ALT $> 3.0 \times \text{ULN}$ with bilirubin $> 2.0 \times \text{ULN}$	Discontinue study drug, except: 
 • Other reason found to explain the findings (such as viral hepatitis A, B, or C, pre-existing or acute liver disease, or another drug capable of causing the observed liver injury) or • Initial findings of cholestasis (elevated serum ALP)

Grade by CTCAE v5.0	Management Recommendation
Skin Rash	

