Grade 1 and 2	No dose modifications required Topical steroid (eg, hydrocortisone 2.5%) and clindamycin cream BID, as needed, and consider oral antibiotic (eg, doxycycline 100 mg BID) for 2 to 4 weeks
Grade ≥ 3	Suspend dose until resolved to \leq Grade 2 and manage as shown above for Grade 1/2 considering additional oral steroids, then: 
 • If resolved ≤ 14 days, resume at the same dose level and consider prophylactic management of skin rash • If resolved > 14 days or re-occurrence, resume at next lower dose level
QT prolongation	
Grade 1	
 • Repeat ECG (triplicates, 2-3 minutes apart) • If QTcF is still on average > 450 ms, check electrolytes and replace to maintain $K \geq 4.0$ mmol/L, $Mg \geq 1.8$ mg/dL (0.9 mmol/L) and $Ca > 8.0$ mg/dL (2.0 mmol/L) and repeat ECG • No dose modifications required
Grade 2	
For first occurrence:
 
 • Repeat ECG (triplicates, 2-3 minutes apart) • Check electrolytes and replace to maintain $K \geq 4.0$ mmol/L, $Mg \geq 1.8$ mg/dL (0.9 mmol/L) and $Ca > 8.0$ mg/dL (2.0 mmol/L) and repeat ECG • If QTcF is still on average > 481 ms, suspend drug until resolved to \leq Grade 1, and then resume at the same dose level 
If re-occurrence:
 
 - Suspend drug until resolved to \leq Grade 1 and then resume at the next lower dose level
Grade 3	
 • Repeat ECG (triplicates, 2-3 minutes apart) • Check electrolytes and replace to maintain $K \geq 4.0$ mmol/L, $Mg \geq 1.8$ mg/dL (0.9 mmol/L) and $Ca > 8.0$ mg/dL (2.0 mmol/L) and repeat ECG • If QTcF is still > 500 ms and/or > 60 ms change from baseline, suspend drug until resolved to \leqGrade 1 and obtain an evaluation by a cardiologist. If study drug can be resumed, it should be at the next lower dose level • If re-occurrence, consider discontinuing the study drug
Grade 4	Discontinue study drug

Grade by CTCAE v5.0	Management Recommendation
Interstitial Lung Disease (ILD) / Pneumonitis (see also Section 6.4.4.3)	
Grade 1	No dose modifications required, consider follow-up at regular intervals as per institutional standards
Grade 2	Suspend dose until resolved to \leq Grade 1, then: 
 • If resolved \leq14 days, maintain dose level • If resolved $>$14 days, resume at the next lower dose level If clinical symptoms persist/worsen despite treatment, consider discontinuing study drug

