Grade 3 and 4	Discontinue study drug
Corneal ulceration	
Grade \geq 3	Discontinue study drug
Other Non-hematologic Toxicities	
Grade 1 and Grade 2	No dose modifications required, administer supportive therapy as indicated
Grade 3	Suspend dose until resolved to \leq Grade 1 or baseline (\leq Grade 2 for toxicities that are manageable by supportive therapy, such as asymptomatic electrolyte changes, dyspepsia, hypertension), then: 
 • If resolved \leq14 days, resume at the same dose level • If resolved $>$14 days or re-occurrence, resume at next lower dose level
Grade 4	Suspend dose until resolved to \leq Grade 1 or baseline, then resume at next lower dose level. Discontinue study drug if re-occurrence or occurrence of an irreversible treatment related clinically significant event.

Abbreviations: ALP=alkaline phosphatase; ALT=alanine aminotransferase; AST=aspartate aminotransferase; BID=twice daily; CTCAE=Common Terminology Criteria for Adverse Events; ECG=electrocardiogram; QD=once daily; QTc=corrected QT interval; QTcF=Fridericia's Correction Formula for corrected QT interval; T-bil=total bilirubin; ULN=upper limit of normal.

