10.1.4.3. Causal Relationship with Study Drug

The causal relationship between an AE and the study drug will be assessed using the following 2-point scale, considering the patient's condition, medical history, concomitant medications, and the temporal relationship between study drug administration and onset of the AE.

1. An AE is considered to be “**Related**” if the event follows a reasonable temporal sequence from administration of study drug and there is a reasonable possibility that at least one of the following conditions is true:
 - A positive dechallenge: This means that the event improves or resolves after the drug is stopped (temporarily or permanently).
 - A positive rechallenge: This means that the event reappears after the drug is restarted.
 - The event cannot be reasonably explained by the patient's clinical state and/or other therapies administered.
 - A single occurrence of an event that is uncommon and known to be strongly associated with drug exposure (eg, angioedema, Stevens-Johnson syndrome).
2. An AE is considered to be “**Not related**” if at least one of the following conditions is true:
 - The event occurred prior to study drug administration.
 - There is no reasonable possibility that the study drug caused the event. (“No reasonable possibility” means there is no evidence to suggest a causal relationship between the study drug and the AE.)
 - The event does not follow a reasonable temporal sequence from administration of study drug and could have been produced by a documented pre-existing condition, concomitant medication, or patient's clinical state.

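### One Grade 4 or higher severe cutaneous reaction halts dosing of new patients, but no rule names the affected patient's treatment, and Table 10 recommends restart if the reaction clears quickly

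*Protocol*

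**What the plan says.** **Study level.** Protocol Section 4.2.4 opens with a general statement, "The study will be stopped in the event of unacceptable toxicities", and then lists events for which one case is enough that "dosing of new patients will be suspended until further review of safety to determine if dosing can resume". The list is not exhaustive. It names three triggers: a death at least possibly related to treatment, a Hy's law case, and, at Grade 4 or higher, "Grade 4 severe cutaneous adverse reactions (Steven-Johnson syndrome, toxic epidermal necrolysis, erythema multiforme, acute generalized exanthematous pustulosis" together with DRESS. The medical monitor, consulting the investigators, then decides whether accrual reopens and whether the protocol needs adjusting.

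**Patient level.** Table 10 (Section 6.2.1.2) gives dosing recommendations for drug-related non-hematologic toxicity. None of the five skin reactions appears in it. Two rows could be applied:

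- Other Non-hematologic Toxicities, Grade 4: hold until Grade 1 or lower or baseline, "then resume at next lower dose level. Discontinue study drug if re-occurrence or occurrence of an irreversible treatment related clinically significant event".
- Skin Rash, Grade 3 or higher: hold until Grade 2 or lower and "manage as shown above for Grade 1/2 considering additional oral steroids". If this takes 14 days or less, "resume at the same dose level and consider prophylactic management of skin rash"; if it takes longer or the rash recurs, go one dose level down.

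For Hy's law, Table 10 has a separate row that begins "Discontinue study drug, except". The exceptions are an alternative explanation or initial cholestasis.

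**General stopping text.** Section 5.4 makes discontinuation mandatory for adverse events judged unacceptable. Its example is a Grade 3 or higher toxicity that has not returned to Grade 1 or baseline within 21 days (Grade 2 suffices if supportive care can manage it). Section 5.4 also allows the physician to decide to stop. Section 6.1 ends treatment at unacceptable toxicity. Section 6.2 accepts holds and reductions made outside the stated criteria.

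**The concern.** The protocol treats one such reaction as grave enough to stop dosing anyone new. For the patient who had it, the only dosing text that applies by its terms is a residual row whose default after recovery is to give the drug again. That row waits for a recurrence, or an irreversible event, before it calls for discontinuation. Whether the drug stops after a first, recovered event therefore depends on the investigator reading a general clause in 5.4 or 6.1 as covering it. The review that 4.2.4 sets off concerns new patients, accrual and protocol changes, so it does not by itself settle this patient's treatment. At stake is the safety of an individual patient in a first-in-human study and consistent handling across sites.

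**Working it through.** No calculation in the plan bears on this point. The check sets the provisions side by side and follows one case through them.

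1. **Does Table 10 apply?** It covers drug-related events. Section 10.1.4.3 lists, among the conditions that support relatedness given reasonable timing, "A single occurrence of an event that is uncommon and known to be strongly associated with drug exposure (eg, angioedema, Stevens-Johnson syndrome". A Stevens-Johnson case could thus be classed as related on one occurrence and come under Table 10. The other four reactions are not named there and would be judged on the general criteria.

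2. **Which grade is exposed?** The trigger is Grade 4 or higher. Grade 5 is fatal, so the question of further dosing arises at Grade 4 only.

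3. **Which row?** The Skin Rash row describes ordinary rash care, so the residual row is the more natural home. Its restart dose is one level down. The Skin Rash row would allow the same dose.

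4. **Which cases reach a restart under the residual row?** All of these must hold: the event is drug-related and non-fatal; it is a first occurrence; it recovers to Grade 1 or baseline; it does so within 21 days, since otherwise the example in 5.4 points to permanent discontinuation; it leaves no irreversible, clinically significant related event; and the investigator does not class it as unacceptable under 5.4 or 6.1.

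5. **How does Table 10 treat other Grade 4 events?** Eight graded categories have a Grade 4 action:
   - discontinue at the first event: bilirubin, AST/ALT, QT prolongation, ILD/pneumonitis, corneal ulceration (5);
   - hold, then go one level down: diarrhea, other non-hematologic (2);
   - hold, with the same dose possible: skin rash (1).

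   5 + 2 + 1 = 8. Neither row that a severe cutaneous reaction could fall under is among the five.

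6. **How do the 4.2.4 triggers map to patient-level rules?** Of the three named triggers, one is death. Of the two non-fatal ones, Hy's law has its own discontinuation row and the skin reactions have none: 1 of 2. The protocol gives no reason for the difference.

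**The case against.** The strongest reply is that 5.4 already handles the case. It is mandatory, whereas Table 10 only recommends. Section 4.2.4 speaks of unacceptable toxicities just before its list, so reading a listed Grade 4 reaction as unacceptable under 5.4 and 6.1 is natural. The 21-day limit removes slow recoveries, and the residual row itself stops the drug for irreversible events. A first case also brings in the medical monitor, and 6.1.2 provides for meetings between Sponsor and investigators when safety issues emerge. An unreviewed restart from the table alone is therefore unlikely.

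Most of this stands, and it sets the limits of the point. A reader might infer that the protocol sends any patient with such a reaction back onto the drug. It does not: the conditions in step 4 of the working are cumulative, and 5.4 lets, and arguably obliges, the investigator to stop. What the reply does not supply is a stated link. Sections 5.4 and 6.1 neither name these reactions nor cite 4.2.4, and 6.2 permits caution without requiring discontinuation. The sponsor did not leave Hy's law to the same general clauses.

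A second objection is that a Grade 4 cut-off is arbitrary if the type of reaction is what makes rechallenge unsafe. That is fair. The threshold proposed below simply matches the trigger in 4.2.4. Going lower is a clinical judgement that these documents do not settle.

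**Conclusion.** The point holds in a limited form and should be corrected. For a drug-related Grade 4 severe cutaneous reaction that recovers to Grade 1 or baseline within 21 days without irreversible harm, the written dosing recommendation is to restart, while the same event halts dosing of new patients. The general stopping clauses probably lead a careful investigator to discontinue, but only by inference.

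The size is structural: one of the two non-fatal triggers in 4.2.4 lacks a patient-level discontinuation row, and five of the eight graded Table 10 categories with a Grade 4 action stop at the first event while the default row does not. A reader might want to turn this into an expected number of cases among the roughly 200 planned patients. The documents give no rate for these reactions, and a rate for any case would not count the smaller group who recover in time and could be restarted, so no such figure is offered.

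The conclusion assumes that the residual row is the applicable default and that the event is judged drug-related. It has no bearing on endpoints, sample size or analysis.

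**What to change.** Add a Table 10 row for the severe cutaneous reactions listed in Section 4.2.4, at Grade 4 or higher and study drug-related, with the action: permanently discontinue TAS3351. State that this row takes precedence over the Skin Rash and Other Non-hematologic rows. Cross-reference it in 4.2.4, so that the study-level trigger points to the patient-level action, and in 5.4, so that it counts as a discontinuation reason.

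The cost is one row, one sentence and two cross-references in a protocol amendment. The downside is that very few patients lose the option of rechallenge after recovery. Grade 3 forms would stay under the existing rows and investigator judgement unless the sponsor chooses on clinical grounds to extend the row.

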4.3. Scientific Rationale for Study Design

The study design of this Phase 1/2 study will allow efficient assessment of the safety and efficacy of TAS3351 in the target population of patients with advanced NSCLC with tumors harboring an acquired C797S *EGFR*mt. The Phase 1 Dose Escalation will use the BOIN design, a simple and well-performing design for Phase 1 oncology trials¹⁵ followed by a Dose Expansion part to confirm the RP2D and explore efficacy. In order to appropriately characterize the PK profile of TAS3351, there will be a PK lead-in for patients enrolled in the Dose Escalation part with a single administration of TAS3351 3 days prior to the start of daily dosing of TAS3351 with subsequent PK sampling.

The Phase 2 part of this study will be a single-arm study of TAS3351 monotherapy in the absence of any approved or well-established standard of care treatment options for these

patients on a potential control arm, highlighting the unmet medical need in this patient population.

In trials of molecularly targeted agents, minimal toxicity may arise over all doses under consideration and higher doses may not result in a greater response.¹⁹ The Phase 1/2 study design employed here could facilitate selection of a dose/regimen with acceptable toxicity that maximizes efficacious response. It allows for faster adaptation and refinement of subsequent parts of the study based on emerging data. It could enhance monitoring of cumulative safety data over time. If Phase 1 data show a favorable benefit/risk profile, the Phase 2 can start to enroll patients right away, which would speed up the drug development in an area of high unmet medical need.²⁰

